## 10.5. Appendix 5: Study Tabular Summary

Parameter Group	Parameter	Value
Trial information	Trial Title	Evaluating the Impact of AGN-190584 on Night-driving Performance
	Clinical Study Sponsor	Allergan Sales, LLC
	Trial Phase Classification	Phase 3b
	Trial Indication	Presbyopia
	Trial Indication Type	Treatment
	Trial Type	Efficacy Safety
	Trial Length	22 to 71 days, with a 30-day screening period
	Planned Country of Investigational Site	Australia
	Planned Number of Enrolled Participants	Approximately 54
	FDA-regulated Device Study	No
	FDA-regulated Drug Study	Yes
	Pediatric Study	No
Participant information	Healthy Participant Indicator	No
	Planned Minimum Age of Participants	40
	Planned Maximum Age of Participants	55
	Sex of Participants	Both
	Stable Disease Minimum Duration	Not specified
Treatments	Investigational Therapy or Treatment	AGN-190584 (pilocarpine HCl 1.25% ophthalmic solution)
	Intervention Type	Drug
	Dose per Administration	1 bilaterally
	Dose Units	Drop
	Dosing Frequency	Once daily
	Route of Administration	Topical eyedrop
Trial design	Study Type	Interventional
	Intervention Model	Crossover
	Planned Number of Arms	2
	Trial Is Randomized	Yes
	Trial Blinding Schema	Double-masked
	Adaptive Design	No

## 10.6. Appendix 6: Contraceptive Guidance and Collection of Pregnancy Information

### Definitions:

#### Woman of Childbearing Potential

A woman is considered fertile following menarche and until becoming postmenopausal unless permanently sterile (see below).

If fertility is unclear (eg, amenorrhea in adolescents or athletes) and a menstrual cycle cannot be confirmed before first dose of study intervention, additional evaluation should be considered.

Women in the following categories are not considered WOCBP

1. Premenarchal
2. Premenopausal female with one of the following:
  - Documented hysterectomy
  - Documented bilateral salpingectomy
  - Documented bilateral oophorectomy

For individuals with permanent infertility due to an alternate medical cause other than the above, (eg, Müllerian agenesis, androgen insensitivity), investigator discretion should be applied to determining study entry.

Note: Documentation can come from the site personnel's: review of the participant's medical records, medical examination, or medical history interview.

3. Postmenopausal female
  - A postmenopausal state is defined as no menses for 12 months without an alternative medical cause.
    - A high FSH level in the postmenopausal range may be used to confirm a postmenopausal state in women not using hormonal contraception or HRT. However, in the absence of 12 months of amenorrhea, confirmation with more than 1 FSH measurement is required.
  - Females on HRT and whose menopausal status is in doubt will be required to use one of the nonestrogen hormonal highly effective contraception methods if they wish to continue their HRT during the study. Otherwise, they must discontinue HRT to allow confirmation of postmenopausal status before study enrollment.

**Contraception Guidance:**

Female Participants

Female participants of childbearing potential are eligible to participate if they agree to use a highly effective or acceptable method of contraception consistently and correctly as described in [Table 10–1](#).

**Table 10–1 Highly Effective and Acceptable Contraceptive Methods**

Highly Effective Contraceptive Methods That Are User Dependenta Failure rate of < 1% per year when used consistently and correctly

Combined (estrogen- and progestogen-containing) hormonal contraception associated with inhibition of ovulation
 
 
• Oral
 
• Intravaginal
 
• Transdermal
 

Progestogen-only hormonal contraception associated with inhibition of ovulation
 
 
• Oral
 
• Injectable
 

Highly Effective Methods That Are User Independenta

 
• Implantable progestogen-only hormonal contraception associated with inhibition of ovulationb
 
• IUD
 
• IUS
 
• Etonogestrel implant (ie, Nexplanon®)
 
• Bilateral tubal occlusion (eg, Essure®, bilateral tubal ligation)
 
• Intrauterine copper contraceptive (ie, ParaGard®)
 

Vasectomized Partner A vasectomized partner is a highly effective contraception method provided that the partner is the sole male sexual partner of the WOCBP and the absence of sperm has been confirmed. If not, an additional highly effective method of contraception should be used.

Sexual Abstinence Sexual abstinence is considered a highly effective method only if defined as refraining from heterosexual intercourse during the entire period of risk associated with the study intervention. The reliability of sexual abstinence needs to be evaluated in relation to the duration of the study and the preferred and usual lifestyle of the participant.

Acceptable Methods Acceptable birth control methods that result in a failure of more than 1% per year include:

 
• Progestogen-only oral hormonal contraception, where inhibition of ovulation is not the primary mode of action
 
• Male or female condom with or without spermicide
 
• Cap, diaphragm, or sponge with spermicide
 
• Nonhormonal intrauterine device
 
 
A combination of male condom with either cap, diaphragm, or sponge with spermicide (double-barrier methods) are also considered acceptable, but not highly effective, birth control methods.

a Typical use failure rates may differ from those when used consistently and correctly. Use should be consistent with local regulations regarding the use of contraceptive methods for participants participating in clinical studies.

### **Pregnancy Testing:**

- WOCBP should only be included after a confirmed menstrual period, a negative highly sensitive urine pregnancy test at screening, and a negative test at Visit 2.
- Additional pregnancy testing should be performed at study exit, and as required locally.
- Pregnancy testing will be performed whenever a menstrual cycle is missed or when pregnancy is otherwise suspected.
- Urine pregnancy testing will be used unless the study site requires the use of serum testing, in which case serum testing will be used.

### **Collection of Pregnancy Information**

#### **Female Participants Who Become Pregnant**

- The investigator will collect pregnancy information on any female participant who becomes pregnant while participating in this study. In the event of pregnancy, the investigator will notify Clinical Pharmacovigilance within 24 hours of the site being made aware by entering the initial information into the EDC system (RAVE®).
- Pregnancies that occur prior to the site having access to the RAVE system, or if RAVE is not operable, should be documented on pregnancy paper forms and emailed (preferred route) or faxed to Clinical Pharmacovigilance within 24 hours of the site being made aware of the pregnancy.
- The participant will be followed to determine the outcome of the pregnancy. The investigator will collect follow-up information on the participant and the neonate and the information will be forwarded to the sponsor. Generally, follow-up will not be required for longer than 6 to 8 weeks beyond the estimated delivery date. Any termination of pregnancy will be reported, regardless of fetal status (presence or absence of anomalies) or indication for the procedure.
- While pregnancy itself is not considered to be an AE or SAE, any pregnancy complication will be reported as an AE or SAE.
- Abnormal pregnancy outcomes (eg, spontaneous abortion, fetal death, stillbirth, congenital anomalies, ectopic pregnancy) or genetic abnormalities (whether leading to an elective abortion or not) are always considered to be SAEs and will be reported as such.
- Any poststudy pregnancy related SAE considered reasonably related to the study intervention by the investigator will be reported to the sponsor as described in Section 8.3.4. While the investigator is not obligated to actively seek this information in former study participants, he or she may learn of an SAE through spontaneous reporting.
- Any female participant who becomes pregnant while participating in the study will discontinue study intervention or be withdrawn from the study.

**10.7. Appendix 7: Night-driving Experience Questionnaire**

**This survey asks questions about your vision during the drive that you just completed.**

*For questions 1-4, please circle the choice that best describes your answer to each question.*

1- I was satisfied with the quality of my vision for driving.	Very dissatisfied	Dissatisfied	Neither satisfied nor dissatisfied	Satisfied	Very satisfied
2- My vision did not impact my confidence in driving.	Not at all	A little	Somewhat	Very	Extremely
3- I noticed a double image around distant objects.	Never	Rarely	Some of the time	Most of the time	All of the time
4- I experienced visual disturbance (glare, halo, starburst) in dim lighting.	Never	Rarely	Some of the time	Most of the time	All of the time
For questions 5-12, please mark an (X) in the box that best describes your answer to each question.	Not difficult at all	A little difficult	Moderately difficult	Very difficult	Extremely difficult
How difficult were the following driving tasks during the drive that you just completed?					
5- Seeing hazards on the road in time to avoid them					
6- Keeping in my lane					
7- Seeing pedestrians at the roadside					
8- Reading the road signs					
9- Judging distances					
10- Reading car gauges (eg, speedometer) without straining my eyes					
11- Adjusting my vision when looking from the road to the speedometer and back					
12- Overall, how difficult was it to see during the driving task?					

1.0 Introduction

This Statistical Analysis Plan (SAP) provides a technical and detailed elaboration of the statistical analyses of the efficacy and safety data as outlined and specified in protocol amendment 1 for Study 1883-306-013 (approved on 15-Apr-2021).

The SAP will not be updated in case of administrative changes or amendments to the protocol unless the changes impact the analysis.

Unless noted otherwise, all analyses will be performed using SAS version 9.4 (SAS Institute Inc, Cary, NC 27513) or later.

2.0 Study Design and Objectives

2.1 Objectives and Hypothesis

The objectives are:

- To evaluate night-driving performance in real-world driving conditions in participants with presbyopia treated with AGN-190584 versus vehicle
- To evaluate safety in participants with presbyopia treated with AGN-190584 versus vehicle

The primary efficacy endpoint is overall composite driving performance Z score approximately 1 hour after study intervention instillation. The null and alternative hypotheses for the primary efficacy endpoint are:

- H_0 : The difference in mean overall composite driving performance Z score between AGN-190584 and vehicle (AGN-190584 minus vehicle) is < -0.25 .
- H_A : The difference in mean overall composite driving performance Z score between AGN-190584 and vehicle (AGN-190584 minus vehicle) is ≥ -0.25 .

2.2 Study Design Overview

This is a single-center, randomized, double-masked, crossover, Phase 3b study evaluating the effect of AGN-190584 compared with vehicle when dosed in both eyes on driving

performance under real-world, night-lighting conditions in participants with objective and subjective evidence of presbyopia.

The study consists of 5 visits (screening [Visit 1], randomization/first dosing [Visit 2], first driving [Visit 3], second dosing [Visit 4], and second driving [Visit 5] visits) with a crossover of AGN-190584 and vehicle. There will be a 7- to 14-day study intervention adaptation period before each driving visit (Visits 3 and 5) and a 7- to 42-day washout period between Visits 3 and 4. Participants will require transport to and from both driving visits.

[figure not shown]
Approximately 54 participants will be enrolled at one study site (Queensland University of Technology, Australia) and approximately 40 participants are expected to complete the study based on an anticipated dropout rate of 25% or less. Participants who prematurely discontinue from the study will not be replaced.

The dosing regimen and schedule for this study are as follows:

Study intervention sequence	Visit 2 through Visit 3	Washout Period	Visit 4 through Visit 5
Sequence 1	AGN-190584		Vehicle
Sequence 2	Vehicle		AGN-190584

The schema of the study is shown in Figure 2-1.

Figure 2-1 Study Schema

2.3 Treatment Assignment and Blinding

Participants will be randomized to the following study intervention sequences in a 1:1 ratio:

- AGN-190584 followed by vehicle
- vehicle followed by AGN-190584

The identity of study intervention will be masked to the participants and the study center.

2.4 Sample Size Determination

The sample size calculation is based on the primary efficacy endpoint. Assuming no difference between treatment groups and variance of 0.11, approximately 40 participants will be required to obtain 90% power for a 1-sided noninferiority test with type 1 error of 0.025 and noninferiority margin of -0.25 units in mean overall composite driving performance Z score. Therefore, approximately 54 participants will be enrolled to achieve 40 participants completing the study assuming an anticipated dropout rate of 25% or less.

3.0 Endpoints

3.1 Primary Endpoint

Primary efficacy endpoint is overall composite driving performance Z score approximately 1 hour after study intervention instillation.

3.2 Other Efficacy Endpoints

- Hazard avoidance
- Road sign recognition
- Road sign recognition distance
- Pedestrian recognition distance
- Lane keeping
- Driving time
- Pupil diameter
- Halometer
- Night-driving experience questionnaire

3.3 Safety Endpoints

- Mesopic/photopic habitual distance visual acuity (HDVA)
- Adverse events (AEs)
- Pregnancy tests for women of childbearing potential (WOCBP)
- Slit-lamp biomicroscopy
- Intraocular pressure (IOP) measurements

4.0 Analysis Populations

The following populations are defined:

Population	Description
Intent-to-Treat (ITT)	The ITT population includes all randomized participants.
Safety	The safety population includes all treated participants who receive ≥ 1 administration of study intervention.

For analyses based on the ITT population, participants will be summarized according to the randomized study intervention. For analyses based on the Safety population, participants will be summarized according to the study intervention they actually receive in each period.

Also, only statistical analyses of safety will be performed by study period as defined in Table 4-1.

Table 4-1 Definition of the Control Period

Period	Start Date	End Date
Period 1	Date of the first dose at Visit 2	
 For participants who do not receive the treatment at Visit 4: the end date is the study exit date. For participants who receive the treatment at Visit 4: the end date is the date when the treatment is received at Visit 4 minus 1 day.
Period 2	Dose date at Visit 4	Study exit date

5.0 Subject Disposition

The total number of participants who were screened, enrolled (randomized), and treated will be summarized. Reasons for exclusion, including screen failure, will be summarized.

A summary of participant accountability will be provided where the number of participants in each of the following categories will be summarized for each intervention group:

- participants randomized in the study;
- participants who took at least one dose of study drug;

- participants who completed protocol-specified treatment;
- participants who prematurely discontinued study drug and reasons for discontinuation;
- participants in each analysis population, as applicable.

Participant disposition will be summarized by study intervention sequence for the entire study and for Period 1 and Period 2.

6.0 Study Drug Duration

For the safety population, duration of treatment will be summarized by study intervention group. Duration of treatment for each intervention group is defined for each participant as the duration of treatment in Period 1 or Period 2, last dose date minus first dose date in each period +1. Duration of treatment will be summarized using the number of participants treated, mean, standard deviation, median, minimum and maximum. In addition, the number and percentage of participants in each treatment duration interval (1 to 7, 8 to 15, and > 15 days) will be summarized by study intervention group.

7.0 Demographics, Baseline Characteristics, Medical History, and Prior/Concomitant Medications

Demographics, medical history, ophthalmic history and prior and concomitant medications will be summarized by study intervention sequence and in total (e.g., across study intervention sequence) for the ITT population. Categorical variables will be summarized with the number and percentage of participants; percentages will be calculated based on the number of non-missing observations. Continuous variables will be summarized with descriptive statistics (number of non-missing observations, mean and standard deviation, median, minimum and maximum).

7.1 Demographics and Baseline Characteristics

Continuous demographic variables include age, weight, height, and body mass index (BMI). Categorical demographic variables include sex, ethnicity, race and age (≤ 50 and > 50 years) when applicable

Demographic parameters will be summarized descriptively by study intervention sequence and in total for the ITT population. Age is calculated from birthdate to the informed consent date in years.

Corrected distance visual acuity (CDVA) and distance-corrected near visual acuity (DCNVA) at baseline will be summarized descriptively by study intervention sequence and in total for the ITT population.

7.2 Medical History

Medical and ophthalmic history data will be coded using Medical Dictionary for Regulatory Activities (MedDRA) dictionary. The actual version of the MedDRA coding dictionary will be noted in the statistical tables and clinical study report.

The number and percentage of participants in each medical history category (by MedDRA system organ class and preferred term) will be summarized in total and by study intervention sequence. The system organ class (SOC) will be presented in alphabetical order, and the preferred terms will be presented in alphabetical order within each SOC. Participants reporting more than one condition/diagnosis will be counted only once in each row (SOC or preferred term).

Ophthalmic history will be summarized similarly. Medical and ophthalmic histories include medical condition prior to Day 1 baseline visit, whether ongoing or resolved.

7.3 Prior and Concomitant Medications

Prior and concomitant medications will be summarized by generic name. A prior medication is defined as any medication taken prior to the date of the first dose of study

drug. A concomitant medication is defined as any medication that started prior to the date of the first dose of study drug and continued to be taken after the first dose of study drug or any medication that started on or after the date of the first dose of study drug. The number and percentage of participants taking medications will be summarized by generic drug name based on the World Health Organization (WHO) Drug Dictionary for both prior and concomitant medications.

The number and percentage of participants reporting prior medications will be summarized by drug generic name in total and by study intervention sequence. If a participant took a specific medication multiple times or took multiple medication within the same generic name, the participant will be counted only once for the generic name.

The number and percentage of participants reporting concomitant medications will be summarized by drug generic name by study intervention group. The listings will be provided for prior and concomitant medications.

7.4 Data Collected but Not Analyzed

Iris color assessment, vital signs, ocular surface disease index, National Eye Institute Visual Function questionnaire 25, fluorescein corneal stain, gonioscopy/angle assessment, binocular mesopic and photopic high contrast, BCDVA and DCNVA assessments, manifest refraction and dilated fundoscopic examination results are collected only at Screening and will not be analyzed. Any clinically significant vital sign findings or abnormal pupil dilation findings will be captured as an adverse event and summarized accordingly.

8.0 Efficacy Analyses

8.1 General Considerations

- The primary analysis will be performed after the database is locked and randomization schedule is released.
- Efficacy endpoints will be analyzed using the ITT population. The 95% confidence intervals will be provided for the primary endpoint.

- Baseline for efficacy is defined as the last nonmissing efficacy assessment before the first dose of study intervention in each period or randomization if no study drug is given when applicable.
- Continuous variables will be summarized by number of participants with observed values (n), mean, standard deviation, median, 1st and 3rd quartiles, minimum, and maximum.
- Categorical variables will be summarized by number of participants with observed values (n), frequency counts (n1) and percent of participants with observed values.

8.2 Handling of Missing Data

Missing continuous and categorical efficacy data will be analyzed based on observed data. Missing values will be not imputed.

8.3 Primary Efficacy Endpoint and Analyses

8.3.1 Primary Efficacy Endpoint

The night-driving evaluation will be performed approximately 1 hour following study intervention instillation at both driving visits.

The overall composite driving performance Z score for a participant is calculated using the average of Z scores for the following component driving measures: percent hazards hit, percent sign recognition and recognition distance, pedestrian recognition distance, lap duration and percent of time outside of the lane (lane-keeping).

A participant's Z score for a given component driving measure is calculated using the mean and standard deviation from the pooled treatment data. Since a lower percent of hazards hit, lower percentage of time outside of the lane and a shorter lap duration is indicative of better performance, the Z scores of these three components are reversed (e.g., $-1 \times Z$ score) before computing the overall driving Z score.

The primary efficacy endpoint is overall composite driving performance Z score approximately 1 hour after study intervention instillation.

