### 8.1.3. Driving Time

Time to complete the road course will be recorded for each run (in minutes and seconds).

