**Figure 8-2 Experimental Pedestrian in Reflective Gear**

### 8.1.6. Composite Driving Z Score

A composite driving Z score will also be derived to capture the overall driving performance of each participant compared with the whole group, as has been used in previous studies (Wood 2002, Wood 2009, Wood 2010, Wood 2014). The composite score is calculated using the average of Z scores for the following component driving measures: percent hazards hit, percent sign recognition and recognition distance, pedestrian recognition distances (pedestrians 1 and 2), and percent of time outside of lane (lane-keeping). The composite score is an important measure to account for differences in how participants prioritize the various driving tasks, where some components may have been performed better to the detriment of other components, and has been used in the previous studies listed above.

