8.3.3 Primary Efficacy Analysis

Primary efficacy endpoint (overall composite driving performance Z score approximately 1 hour after study intervention instillation) will be analyzed using a linear mixed-effects model with repeated measures (MMRM).

The model will use overall composite driving performance Z score approximately 1 hour after study intervention instillation as dependent variable, include study intervention group (AGN-190584, vehicle), study intervention sequence (Sequence 1: AGN-190584 followed by vehicle, Sequence 2: vehicle followed by AGN-190584), and study period (Period 1, Period 2) as fixed effects and participant nested within sequence of testing as a random effect. The covariance structure to model the within-participant correlation error structure will be unstructured. If the unstructured covariance matrix results in a lack of convergence, compound symmetry covariance structure will be used. The Kenward-Roger method will be used to estimate the denominator degrees of freedom.

The least-square (LS) mean and 95% CI will be provided for each study intervention (AGN-190584, or vehicle) in overall composite driving performance driving Z score.

The comparison between the two study interventions (AGN-190584 vs. vehicle) will be performed by providing LS mean and 95% CI for the between-group difference in the overall composite driving performance Z score. Noninferiority of AGN-190584 will be concluded if the lower bound of the 95% CI of the least square mean difference between AGN-190584 and vehicle is greater than -0.25.

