Appendix D. Changes to Protocol-planned Analyses

There are no changes from the protocol-planned analyses.

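### The SAP adds sign-reversed lap duration to the primary composite Z score, the protocol leaves it out, and the SAP declares no change

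*SAP*

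**What the plan says.** SAP section 1.0 presents the plan as elaborating the analyses "as outlined and specified in protocol amendment 1". SAP section 8.3.1 then averages Z scores for "percent hazards hit, percent sign recognition and recognition distance, pedestrian recognition distance, lap duration and percent of time outside of the lane (lane-keeping". Each Z score uses the mean and standard deviation of the two treatments pooled. Three are multiplied by -1: hazards hit, time out of lane and lap duration, the last because "a shorter lap duration is indicative of better performance". Under section 8.3.3, noninferiority is concluded if the "lower bound of the 95% CI of the least square mean difference between AGN-190584 and vehicle is greater than -0.25", and section 11.0 confirms that this is the only hypothesis.

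Protocol section 8.1.6 lists hazards hit, sign recognition (percentage and distance), and "pedestrian recognition distances (pedestrians 1 and 2), and percent of time outside of lane (lane-keeping". There is no time measure and no mention of sign reversal. Driving time has its own section, 8.1.3: "Time to complete the road course will be recorded for each run (in minutes and seconds". Protocol section 9.4.1.1 places it among the other efficacy analyses, and so do SAP section 3.2 and Table 8-1.

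SAP Appendix D nevertheless states: "There are no changes from the protocol-planned analyses".

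Both documents size the trial on the same figures. SAP section 2.4 reads "Assuming no difference between treatment groups and variance of 0.11, approximately 40 participants will be required to obtain 90% power", with a margin of -0.25, and Protocol section 9.2 says the same.

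**The concern.** The protocol spells out its component list, so adding a component changes the endpoint rather than filling in a detail. The SAP gives a reason for the reversal and counts lap duration among three reversed components, so this is not a typing slip. Appendix D and SAP section 8.3.1 cannot both be right while Protocol section 8.1.6 stands. The protocol's summary of changes for Amendment 1 does not mention section 8.1.6, so it offers no explanation, but the point rests on the current texts.

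Protocol section 8.1.6 justifies the composite as allowing for drivers who do one task better at the expense of another, and speed is an obvious such trade-off. A driver who slows down to see better is penalised only under the SAP. A driver who speeds up is rewarded only under the SAP and can thereby offset worse hazard, sign, pedestrian or lane scores. Each document attaches the same 0.11 and -0.25 to its own composite, and neither says which component list those figures were derived for.

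**Working it through.** **1. The two lists side by side**

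| Component | Protocol 8.1.6 | SAP 8.3.1 |
|---|---|---|
| Percent hazards hit | yes | yes, reversed |
| Percent signs recognised | yes | yes |
| Sign recognition distance | yes | yes |
| Pedestrian recognition distance | yes, pedestrians 1 and 2 | yes, number not stated |
| Time out of lane | yes | yes, reversed |
| Lap duration | **no** | **yes, reversed** |

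Neither document says whether the two pedestrians give one Z score or two. The protocol composite therefore has k = 5 or 6 scores and the SAP composite k + 1 = 6 or 7. That is an ambiguity, not a shown change.

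**2. The plan's own sample size**

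Inputs (Protocol 9.2, SAP 2.4): variance 0.11, margin -0.25, true difference 0, one-sided alpha 0.025, 90% power, 40 completers.

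- Reading 0.11 as within-participant variance, the variance of the difference is 2 x 0.11 = 0.22.
- SE = sqrt(0.22/40) = 0.0742. With t(38, 0.975) = 2.024, power is 0.907 and the required N is 40.
- Enrolment: 40/(1 - 0.25) = 53.3, rounded up to 54.

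The stated figures reproduce. Reading 0.11 as the variance of the paired difference gives N = 21, which does not.

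- CI half-width: 2.024 x 0.0742 = 0.150.
- Noninferiority needs an estimate above -0.25 + 0.150 = -0.100.

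**3. Effect of the extra component**

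Let d be the difference on the protocol composite and L the lap-duration difference after reversal (positive = faster on drug). The SAP difference is (k x d + L)/(k + 1). Lap duration has weight 0 in the protocol and 1/6 or 1/7 in the SAP.

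**4. If lap duration is unaffected (L = 0)**

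- At d = -0.25 the SAP difference is -0.25 x 5/6 = -0.208 or -0.25 x 6/7 = -0.214.
- The SAP margin of -0.25 then tolerates a protocol-composite loss of 0.25 x 6/5 = 0.300 or 0.25 x 7/6 = 0.292.
- Chance of concluding noninferiority at d = -0.25 with 40 completers (noncentral t, 38 df): 0.079 (k = 5) or 0.068 (k = 6) with difference variance 0.22. It is 0.096 or 0.079 if that variance falls to 0.22 x (k/(k + 1))^2, the value if lap duration adds no variance or covariance. The nominal figure is 0.025.

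**5. Can the verdict differ?**

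Assumed shifts in component SDs, for illustration only. The half-width is 0.150 for both composites.

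| | Protocol components | L | Protocol bound | SAP bound (1/6; 1/7) |
|---|---|---|---|---|
| (a) | -0.15 each | +0.30 | -0.150 - 0.150 = -0.300, fail | -0.075 - 0.150 = -0.225; -0.086 - 0.150 = -0.236, pass |
| (b) | -0.05 each | -0.60 | -0.050 - 0.150 = -0.200, pass | -0.142 - 0.150 = -0.292; -0.129 - 0.150 = -0.279, fail |

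Break-even is L = -0.100(k + 1) - k x d. In (a) the SAP version passes once L exceeds about +0.15 (1/6) or +0.20 (1/7). In (b) it fails once L is below about -0.35 or -0.40.

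**6. Sensitivity**

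- 54 completers, half-width 0.128: (a) -0.278 against -0.203; -0.214. (b) -0.178 against -0.270; -0.257. Both reverse.
- 0.11 as paired-difference variance, n = 40, half-width 0.106: (a) -0.256 against -0.181; -0.192, reverses. (b) -0.156 against -0.248; -0.235, does not.
- Same reading, n = 54, half-width 0.091: all bounds lie above -0.25, so neither reverses.

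**The case against.** Driving time is not a new measure. The protocol names it as a driving-performance metric, and Protocol section 9 leaves detailed methods to a SAP that must be final before database lock and unmasking. The SAP fixes the direction and standardisation of lap duration, so within its own definition the type I error is not inflated, and nothing suggests a data-driven choice. SAP Table 8-1 summarises driving time and the other components by treatment, so an offset would be visible. All of this is fair, but none of it reconciles an explicit protocol list with a longer SAP list and a statement of no change. The component summaries are descriptive; the verdict rests on the composite.

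The shifts in step 5 can also be challenged. No document supports them, and in (b) lap duration moves 12 times as far as every other component. A pooled SD includes between-participant spread, so 0.60 SD is a large treatment shift in a crossover. The equal half-width matters too. If the SAP composite's half-width shrinks by k/(k + 1), then with 54 completers it is 0.107 or 0.110, the SAP bounds in (b) are about -0.248 and -0.238, and (b) no longer reverses. Both reversals at n = 40 survive that limit, and 54 completers would mean no dropout at all. These points stand: the scenarios show that the verdict can differ, not that it is likely to.

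Finally, a sensitivity analysis on the composite not chosen goes beyond what is needed to remove the contradiction. That is true, but it costs one model run and shows whether the choice mattered.

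**Conclusion.** The concern holds. The component list of the only tested endpoint depends on which document is followed, and Appendix D is wrong as written. This must be settled before unmasking. The sample-size arithmetic itself is sound.

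The textual contradiction needs no assumption. Its size does. A weight of 1/6 or 1/7 assumes equal averaging, as the SAP states. The rise from 2.5% to about 7% to 10% assumes no drug effect on lap duration, 40 completers and 0.11 as within-participant variance. The reversals in either direction depend on the assumed shifts and, for some, on the variance reading and the number of completers. The actual direction of the effect is unknown.

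**What to change.** Before unmasking:

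- Fix one component list for both documents. State how many Z scores the two pedestrians contribute, and define lap duration, which I take to be the driving time per run of Protocol section 8.1.3.
- Either remove lap duration from SAP section 8.3.1, or keep it, amend Protocol section 8.1.6 and declare the change in SAP Appendix D.
- State that the 0.11 variance and the -0.25 margin refer to the chosen composite.
- Prespecify the other version as a sensitivity analysis with the same mixed model.

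The cost is SAP wording, a protocol amendment if lap duration stays, and one extra model run. No new data are needed if lap duration is the driving time already recorded.
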